4.4.2 All adverse events

The subject incidence of AEs reported during the screening phase will be summarised by all AEs, Deaths, SAEs, and withdrawal from study due to AE.

The subject incidence of treatment emergent AEs will be summarized by treatment group in the following ways:

- All AEs, (by severity)
- AEs classified as related to study drug
- Deaths
- SAEs (by severity, and excluding where the outcome was death)
- AEs leading to study discontinuation

The subject incidence of treatment emergent AEs will be summarized separately by SOC, PT and treatment group for the double-blind treatment period.

The subject incidence of the most common (reported in at least 2% of the subjects in any treatment group) treatment emergent AEs will be presented by SOC, PT and treatment group. Also, the subject incidence of treatment emergent AEs will be presented by PT, intensity and treatment group. The subject incidence of ischaemic cardiovascular AEs will also be presented by PT. Ischaemic cardiovascular AEs will be identified using key words of ‘myocardial infarction’, ‘acute coronary syndrome’, ‘unstable angina’(or angina unstable), ‘stroke’ (excluding heat stroke), ‘cerebrovascular accident’, ‘cerebral infarction’. A subject listing of all reported AEs during the screening and the double-blind treatment period will be produced.

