## **Duration of treatment**

Rosuvastatin or placebo will be administered once daily for a 104-week treatment period.

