### **3.9 Discontinuation of investigational product**

Subjects may be discontinued from investigational product in the following situations, at the discretion of the investigator(s):

- Subject decision. The subject is at any time free to discontinue treatment, without prejudice to further treatment.
- An AE that in the opinion of the investigator warrants subject withdrawal.
- Severe non-compliance with the study protocol.
- Withdrawal of informed consent.
- CK >10 x ULN accompanied by muscle pain, tenderness, or weakness; see Appendix D for management of increased creatine kinase.
- ALT or AST >3 x ULN; see Appendix C for further instruction on cases of increases in liver biochemistry and evaluation of Hy's Law.
- Deterioration in the subject's condition that in the opinion of the investigator warrants subject withdrawal.
- At investigator's discretion.
- Development of a condition that made the subject high-risk, such as clinical atherosclerotic disease (MI, transient ischemic attack, stroke, angina pectoris, symptomatic CAD, peripheral arterial disease, abdominal aortic aneurysm) or diabetes mellitus.

Subjects will be monitored to ensure that they are within the entry criteria limits for LDL-C throughout the study. Subjects will be discontinued from the treatment in 1 of 2 circumstances based on a subject's inclusion criteria:

1. Subjects with no additional CVD risk factors other than age and hypertension, and subjects without hypertension who have 3 or more other risk factors (including age) will be discontinued from the treatment if their LDL-C levels are  $\geq 160$  mg/dL (4.1 mmol/L) on 2 consecutive visits during the study.
2. Subjects without hypertension who have fewer than 3 other risk factors (including age) will be discontinued from the treatment if their LDL-C levels are  $\geq 190$  mg/dL (4.9 mmol/L) on 2 consecutive visits during the study.

The results of the LDL-C determinations will remain unblinded to the central laboratory but will be blinded to the investigator and site personnel after screening. A flag on the central laboratory report will notify the investigator that the subject should be removed from the study. The subject will be discontinued from the study and complete the Early Termination visit procedures. Subsequent treatment will be advised by the investigator based on local guidelines.

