### **4.3 Follow-up period**

A follow-up period is not planned for this study.

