### **6.3 Recording of adverse events**

#### **6.3.1 Time period for collection of adverse events**

All AEs, including SAEs, will be collected from the time of signature of the informed consent throughout the treatment period and within 10 days after last dose of study drug.

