4.4.4 Serious adverse events

The subject incidence of treatment emergent SAEs will be presented by SOC, PT and treatment group. In addition, the subject incidence of related treatment emergent SAEs will be presented by SOC, PT, and treatment group for the safety analysis. A listing of all SAEs during screening and double-blind treatment period will be produced. If we cannot determine whether an AE is serious, it will be considered an SAE.

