4.6.4 Post-dosing Safety Observations

The following conventions are for the safety analysis during the 104-week randomized double-blind treatment period.

Randomized treatment period safety observations will be listed regardless of whether the subject was taking blinded study drug. However, safety observations will not contribute to summaries if the subject's last dose of blinded drug was as follows:

- All AEs, including SAEs, will be summarized only if their onset dates were within 10 days after last dose of study drug.
- Vital signs, physical examination, safety laboratory and ECG results will be summarized only if measured on or before the 14th day after the last blinded drug dosing date.

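### Adverse-event tables use crude subject percentages to 10 days after last dose, with no person-time rate beside them, although the LDL-C removal rule could shorten placebo time at risk

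*SAP*

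**What the plan says.** **Measure.** SAP 4.4.2 states: "The subject incidence of treatment emergent AEs will be summarized by treatment group in the following ways". The list covers all AEs, related AEs, deaths, SAEs and AEs leading to discontinuation; ischaemic cardiovascular AEs are added as subject incidence by preferred term. SAP 4.4.4 does the same for SAEs: "The subject incidence of treatment emergent SAEs will be presented by SOC, PT and treatment group". SAP 4.4.5 covers related AEs, and 4.4.6 summarizes AEs leading to treatment discontinuation by SOC, PT and arm. No visible text plans a person-time rate or a time-to-first-event summary.

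**Window.** Protocol 6.3.1 collects AEs from consent "throughout the treatment period and within 10 days after last dose of study drug". SAP 4.6.4 adds: "All AEs, including SAEs, will be summarized only if their onset dates were within 10 days after last dose of study drug". Protocol 4.3 says: "A follow-up period is not planned for this study".

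**Removal rule.** Protocol 3.9 says that subjects "will be discontinued from the treatment if their LDL-C levels are" at or above 160 or 190 mg/dL, according to risk group, on two consecutive visits. It continues: "A flag on the central laboratory report will notify the investigator that the subject should be removed from the study". The subject then completes the Early Termination visit.

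**What partly helps.** SAP 4.2.5.1 tabulates duration of exposure by arm, in bands, cumulatively and as summary statistics, and again for premature discontinuers. SAP 4.2.1 gives discontinuation reasons by arm. Safety is descriptive, with no formal tests (Protocol 8.5.3, SAP 4.4).

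**The concern.** The safety objective is a comparison with placebo over 104 weeks. A percentage of subjects with an event is a fair basis for that comparison only if both arms are watched for about the same time. Here observation is tied to dosing, and one stopping rule is tied to the variable that the drug changes. Subjects enter with LDL-C from 120 mg/dL up to the same limits that later trigger removal. Protocol 1.1 describes rosuvastatin as effective at lowering LDL-C, so few rosuvastatin subjects should reach the limit twice running, while some placebo subjects may.

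If placebo time at risk is shorter, equal event rates produce unequal percentages. AE and SAE frequencies on rosuvastatin would look somewhat too high relative to placebo, and any reduction in ischaemic cardiovascular AEs would look somewhat too small. The exposure tables might show the imbalance, but exposure is never used as a denominator. A reader cannot rebuild time to first event from exposure bands.

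**Working it through.** The visible text gives no AE rate, removal rate or exposure by arm, so there is no stated figure to reproduce.

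**Inputs from the documents**
- Treatment: 104 weeks (Protocol synopsis, Duration of treatment). AE window: last dose + 10 days, that is + 10/7 = 1.43 weeks.
- Post-baseline lipid samples: weeks 6, 13, 39, 65, 91 and end of treatment (SAP 1.2). Counting post-baseline samples only, removal is first possible at week 13.
- 543 randomized 1:1, about 271 per arm.

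**Step 1. Exposure ratio under an assumed LDL-C distribution.** Let f be the share of placebo subjects removed and s their mean stopping week, with full exposure on active:

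ratio = 104 / [104 − f × (104 − s)]

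The removal rule was simulated with assumed inputs: LDL-C mean 135 or 150 mg/dL, SD 20 mg/dL, within-person CV 8% or 11%, the two limits equally common, the entry screen applied, and drift of 0 or 2 mg/dL per year. About 4% to 14% of placebo subjects were removed, at a mean of 40 to 47 weeks. The formula brackets the result:
- f = 4.5%, s = 47: 104 / (104 − 2.57) = 1.03
- f = 14%, s = 40: 104 / (104 − 8.96) = 1.09

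A wider set of assumptions removed 5% to 17% at a mean of 40 to 48 weeks and gave ratios of 1.028 to 1.107.

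**Step 2. From exposure to crude incidence.** Take the same constant hazard λ in both arms and an assumed SAE incidence of 10% at full exposure:

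λ = −ln(0.90) / 105.43 = 0.000999 per week

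For placebo stops spread evenly over weeks 13, 39, 65 and 91, incidence to stop + 10 days is 1.43%, 3.96%, 6.42% and 8.82%, mean 5.16%. Placebo incidence is (1 − f) × 10% + f × 5.16%.

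| f (placebo only) | Placebo incidence | Apparent ratio, spread | All stop week 13 | All stop week 91 |
|---|---|---|---|---|
| 2% | 9.90% | 1.01 | 1.02 | 1.00 |
| 5% | 9.76% | 1.02 | 1.05 | 1.01 |
| 10% | 9.52% | 1.05 | 1.09 | 1.01 |
| 30% | 8.55% | 1.17 | 1.35 | 1.04 |

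The 30% row is a stress test; the simulated removal share did not exceed 17%. For common events the ratio is smaller: with 60% any-AE incidence and spread stops, f = 5% to 30% gives 1.02 to 1.14.

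**Step 3. Allow active-arm stopping.** Same SAE model, stops spread:
- active 5%, placebo 10%: 1.03
- active 10%, placebo 10%: 1.00
- active 10%, placebo 5%: 0.98

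The sign therefore depends on both arms.

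**Step 4. Size in subjects.** At 10% incidence, a ratio of 1.03 means 10 − 10/1.03 = 0.29 points, or 0.8 of 271 subjects. A ratio of 1.09 means 10 − 10/1.09 = 0.83 points, or 2.2 subjects. The 95% half-width for the arm difference is 1.96 × √(2 × 0.10 × 0.90 / 271) = 5.1 points.

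**Step 5. Effect of the fix.** Dividing first events by person-time at risk gives an expected ratio of 1.00 for every f and stopping pattern above, provided the hazard is constant and equal in both arms and removal is unrelated to AE risk. If instead AEs cluster before removals begin, crude incidence is already unbiased, and dividing by longer active exposure gives a false ratio of about 1/1.03 to 1/1.11, that is 0.97 to 0.90.

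**The case against.** The strongest case against the point has four parts.

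- **Direction is not fixed.** Protocol 3.9 also lists AEs, symptomatic CK above 10 × ULN and ALT/AST above 3 × ULN as stopping reasons, and these can shorten rosuvastatin exposure. This stands. It rules out a claim that the bias must run against the drug, but it does not remove the case for person-time rates, which adjust for unequal follow-up in either direction.
- **The size rests on assumed inputs and is small.** This also stands. The documents give no LDL-C distribution or removal rate, and the sample-size text that might state dropout is redacted, so its absence is not a fault of the plan. A shift of one or two subjects with an SAE is well inside sampling error.
- **Safety is descriptive and exposure is tabulated.** No test or decision rule is affected, and an imbalance would be visible. But the arm percentages are what readers will compare, and showing an imbalance does not correct for it.
- **Rates can mislead too.** If drug-related events come early, dividing by longer active exposure understates them. This stands, and it limits the fix to a supplement.

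A reader might infer that the plan would make any inert drug look harmful. It would not: a drug with no LDL-C effect would trigger the removal rule equally in both arms. The scenario needs a drug that lowers LDL-C and has no effect on AEs. A reader might also infer that every safety comparison is cut at 10 days. The deaths summary in SAP 4.4.3 takes all deaths recorded on the named CRF pages and does not restate that limit.

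**Conclusion.** The gap is real and modest. The AE tables are crude subject incidence, the window closes 10 days after last dose, and one removal rule should fall mainly on placebo, yet nothing in the visible text adjusts for time at risk. With full active-arm exposure and the assumed LDL-C inputs, a true ratio of 1.00 for uncommon events would show as about 1.03 to 1.09, or up to about 1.11 with stronger assumptions. It is negligible if about 2% are removed or removals come late, and nil or reversed if active-arm stopping matches or exceeds placebo stopping.

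The documents do not support saying that the plan will overstate harm, only that it could. Nor do they support replacing crude incidence by rates as the sole basis for between-arm statements. The point is a cheap improvement to the presentation of safety data, not an error that invalidates it.

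**What to change.** In SAP 4.4.2 and 4.4.4 to 4.4.6:

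- Keep the planned crude counts and percentages.
- As a supplement, add subjects with event per 100 subject-years at risk, with time running from first dose to the earlier of first event and last dose + 10 days. Do this for overall treatment-emergent AEs, SAEs, AEs leading to discontinuation, ischaemic cardiovascular AEs, and preferred terms reported in at least 2% of subjects in any arm.
- State that both measures are read together when exposure differs by arm, with reference to the exposure tables in SAP 4.2.5.1.
- State that the rates assume a roughly constant hazard and can understate early drug-related events.

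The cost is a few lines of SAP text and one column in existing tables, computed from dosing and AE onset dates that are already collected. The wording should be settled before unblinding. No change to trial conduct or to the removal rule is implied.

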Although CHD and stroke have some differences in origin, atherosclerosis is a common pathophysiological basis for both. Hypertension, hyperlipidemia, smoking, diabetes mellitus, obesity, age, and sex are widely accepted as major risk factors for atherosclerosis, CHD, and ischemic stroke (NCEP 2001). To properly consider the potential hazards of dyslipidemia on the Chinese population, Chinese scholars advocate using ICVD risk to represent integrated cardiovascular risk and Chinese prevalence characteristics (Wu et al 2004). The concept of integrating the risk of CHD and ischemic stroke into a single model and then using the resulting model in clinical practice is particularly valuable in countries where stroke risk is high, as it is in China. The 2007 China Adult Dyslipidemia Management Guidelines introduced a system of risk assessment that can be employed in subjects with/without existing CHD (or a CHD risk equivalent) and with/without hypertension by counting categorical risk factors (see Appendix F). Combining this risk assessment system with blood lipid levels allows CVD risk to be comprehensively estimated, allowing stratification of risk and guiding treatment. The risk stratification scheme singles out hypertension to reflect the characteristics of Chinese clinical practice.

In the present study, classification of patient risk and definition of therapeutic goals for LDL-C will be based on the 2007 China Adult Dyslipidemia Management Guidelines. The 10-year ICVD risk is equivalent to approximately 5% to 10% when fasting LDL-C is  $\geq 120$  mg/dL (3.1 mmol/L) and  $< 160$  mg/dL (4.1 mmol/L) for subjects with only hypertension (defined as blood pressure  $\geq 140/90$  mmHg or being on antihypertensive treatment) and age as CVD risk factors, and subjects without hypertension who have 3 or more other risk factors (including age). The 10-year ICVD risk is equivalent to  $< 5\%$  when LDL-C is  $\geq 120$  mg/dL (3.1 mmol/L) and  $< 190$  mg/dL (4.9 mmol/L) for subjects without hypertension who have fewer than 3 other risk factors (including age). The above-mentioned subjects will be the target patient population for current study.

This subject population largely overlaps with the subject population in the METEOR study, and the treatment recommendation/goals are similar, following the local guideline in Chinese and NCEP ATP III in METEOR.

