4.4.3 Deaths

All deaths recorded on the TERM page, the AE page, or SAE page (with a death date, cause of death, outcome or SAE categorization present) of the CRF will be considered a death in the analyses. All deaths will be summarized by SOC and PT for the safety analysis. A listing of all deaths during screening and double-blind treatment period will be produced.

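### The key words for 'ischaemic cardiovascular AEs' in SAP 4.4.2 do not fit that label: they admit haemorrhagic stroke and miss transient ischaemic attack and angina other than unstable

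*SAP*

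**What the plan says.** SAP 4.4.2 plans one grouped summary of clinical cardiovascular events: "The subject incidence of ischaemic cardiovascular AEs will also be presented by PT". The group is defined by a text search: "Ischaemic cardiovascular AEs will be identified using key words of" six concepts, namely myocardial infarction, acute coronary syndrome, unstable angina (in either word order), stroke, cerebrovascular accident and cerebral infarction. One qualifier is attached, to the word stroke: "excluding heat stroke". The SAP amendment history shows that this definition was revised on 01Feb2019.

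Two protocol sections bear on what such a group might contain:

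- Protocol 3.9, on stopping the investigational product, gives examples of conditions that make a subject high-risk: "clinical atherosclerotic disease (MI, transient ischemic attack, stroke, angina pectoris, symptomatic CAD, peripheral arterial disease, abdominal aortic aneurysm". Exclusion criterion 5 in Protocol 3.2 also names angina, transient ischaemic attack and symptomatic coronary artery disease as evidence of atherosclerotic disease.
- Protocol 1.2 explains the risk concept used for eligibility and stratification: "The concept of integrating the risk of CHD and ischemic stroke into a single model".

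Other tables also show these events. SAP 4.4.2 adds that "The subject incidence of treatment emergent AEs will be summarized separately by SOC, PT and treatment group for the double-blind treatment period". SAP 4.4.4 states that "The subject incidence of treatment emergent SAEs will be presented by SOC, PT and treatment group", and SAP 4.4.3 that "All deaths will be summarized by SOC and PT for the safety analysis". SAP 4.4.6 tabulates treatment-emergent events leading to discontinuation by system organ class, preferred term and treatment group. SAP 4.4 makes all safety summaries descriptive, without formal comparison.

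**The concern.** The group's label and its search rule do not agree. The heat-stroke exclusion shows the authors saw that the bare word *stroke* catches too much, but nothing keeps out a stroke that is haemorrhagic by name. In the other direction, a transient ischaemic attack is ischaemic by name and angina is a manifestation of coronary disease. Neither is found by the search unless the angina is recorded as unstable. No section of the SAP explains where the boundary was drawn.

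The primary endpoint is carotid wall thickness, which Protocol 1.1 justifies as a surrogate marker for cardiovascular events. A reader who wants clinical context will look first at the one summary labelled ischaemic. Display by preferred term lets that reader spot a row that should not be there. It cannot show a row that is missing. Rebuilding the group from the full adverse-event tables would then happen after unblinding, when the choice of terms is no longer neutral.

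**Working it through.** The plan states no figure on this point, so there is nothing to reproduce. The check is to apply the search rule as written.

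**Inputs.** The SAP 4.4.2 key words (seven strings, because unstable angina is given in two word orders); the heat-stroke exclusion; the seven conditions in Protocol 3.9; and a few illustrative event terms that are assumed and do not come from the documents.

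**Rule applied.** A term is counted if it contains any key word, ignoring case, and is not heat stroke. The SAP does not say which field is searched or how a match is decided, so this simple containment rule is an assumption.

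**Step 1: the seven conditions in Protocol 3.9.**

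| Condition | Matched? |
|---|---|
| Myocardial infarction | Yes |
| Stroke | Yes |
| Transient ischaemic attack | No |
| Angina pectoris | No |
| Symptomatic coronary artery disease | No |
| Peripheral arterial disease | No |
| Abdominal aortic aneurysm | No |

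Two of seven are matched and five are missed.

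**Step 2: illustrative stroke terms (assumed).**

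| Term | Matched? |
|---|---|
| Ischaemic stroke | Yes |
| Haemorrhagic stroke | Yes |
| Cerebrovascular accident (type not given) | Yes |
| Cerebral haemorrhage | No |
| Subarachnoid haemorrhage | No |
| Heat stroke | No |

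A haemorrhagic event therefore enters only if its term contains *stroke* or *cerebrovascular accident*. Whether an intracranial bleed is in or out depends on how it was worded or coded.

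**Step 3: set the result against the protocol's coronary-plus-ischaemic-stroke concept (Protocol 1.2).** On that concept haemorrhagic stroke falls outside, but a term naming it is admitted. Angina and symptomatic coronary artery disease fall under coronary disease, but only the unstable form of angina is searched for. Peripheral arterial disease is not part of the concept, so its absence is consistent with it.

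**Step 4: try the reading as an acute-event list.** Infarction, acute coronary syndrome, unstable angina and stroke make a coherent acute set. That would explain leaving out stable angina. It would not explain leaving out transient ischaemic attack, which is acute, and it would not explain admitting haemorrhagic stroke under an ischaemic label. Neither the label nor the text says the list is meant to be acute only.

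**The case against.** The strongest reply is that the documents nowhere define which events this group must contain. The Protocol 3.9 list serves decisions about stopping treatment; it is not an adverse-event grouping, and it says plain stroke without an ischaemic qualifier. Using 3.9 to add events and the Protocol 1.2 concept to remove them applies two standards. The list was revised deliberately in February 2019, and Protocol 8.1 requires SAP amendments to be final before unblinding, so the key words are already fixed in advance.

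Much of this stands, and it rules out several stronger readings that a reader might infer:

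- *That this is the trial's only clinical-event table.* It is not. All treatment-emergent events, serious events, deaths and events leading to discontinuation are each tabulated by preferred term. A subject who stopped treatment because of a transient ischaemic attack, recorded as such, would appear in the SAP 4.4.6 table. It is only the sole *grouped* ischaemic summary.
- *That haemorrhagic strokes as a class are counted.* Only terms containing a key word are. Cerebral and subarachnoid haemorrhage are not matched, and a haemorrhagic stroke row would be visible and separable. The SAP promises no pooled total.
- *That peripheral arterial disease must be added.* It lies outside the coronary-plus-ischaemic-stroke concept, so leaving it out is defensible.
- *That the error can be sized.* One might take a 10-year risk of 5% to 10% with constant hazard. The 2-year risk is then 1 − (1 − p)^0.2: 1 − 0.95^0.2 = 1.02% and 1 − 0.90^0.2 = 2.09%, or 5.5 to 11.3 events in 543 subjects. Two or three misplaced events would then be about 18% (2/11.3) to 55% (3/5.5). But subjects below 5% risk are also enrolled, full two-year follow-up of everyone is assumed, and the two or three is a guess. The documents do not support this range.

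What the reply does not answer is the mismatch itself. On either natural reading of the label, a term naming haemorrhagic stroke should be out and transient ischaemic attack needs at least a stated reason for its absence. Fixing the key words in advance also does not fix the list of terms they match.

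**Conclusion.** The point holds in limited form. Followed as written, the rule can put a non-ischaemic event into a group labelled ischaemic. It also leaves out transient ischaemic attack and angina other than unstable, both of which the protocol treats as atherosclerotic disease. The result could be a mislabelled and incomplete ischaemic incidence in the one grouped summary of such events.

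The consequence is small. The summary is descriptive, carries no hypothesis or alpha, and leaves the primary and secondary efficacy conclusions untouched. Every omitted event that is recorded as treatment-emergent can still be found in another table. The size of any miscount cannot be computed, because the documents give neither event counts nor a list of reported terms.

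The conclusion assumes that the search is a plain text match and that events could be recorded under terms like those in the working. It does not require that any such event occurred. It would be wrong to infer from this that the trial's cardiovascular safety reporting as a whole is deficient.

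**What to change.** In SAP 4.4.2:

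1. Exclude haemorrhagic stroke terms as well as heat stroke. An unspecified cerebrovascular accident cannot be typed from its term alone; it can stay as its own row.
2. Add transient ischaemic attack and angina pectoris or symptomatic coronary artery disease to the search, shown as separate preferred-term rows so that the narrower acute-event set can still be read on its own.
3. State that the search runs over all reported preferred terms, and fix the resulting list of matched terms before unblinding.

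Peripheral arterial disease is optional; if it stays out, one sentence citing the coronary-plus-ischaemic-stroke concept is enough.

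The cost is a few lines of SAP wording and one search list, with no new data collection. The small downside is that some softer events will appear in the table, which the separate rows make plain.
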